6.6. Dosages, dosage modifications and method of administration

Each sachet of WholeFiber™ consists of 10 grams of WholeFiber™. Subjects will consume 2 sachets per day for 5 weeks, resulting in 20 g/day of WholeFiber™. In the first week of the intervention period the participants consume 1 sachet per day, resulting in 10 g/day of WholeFiber™. The participant will be advised to add the product to various dishes according to one's taste. Subjects can use WholeFiber™ in the recipes if they wish, but it can also be consumed as is. Advice will be given on consumption of WholeFiber™.

6.7. Preparation and labelling of Investigational Medicinal Product

Preparation and the labeling of WholeFiber™ (350 g) will be conducted at WholeFiber Holding BV (Espel, the Netherlands), the same packaging is used as the commercially available product from WholeFiber Holding BV. Packaging of the individual sachets (supplemented by WholeFiber™) will be performed by the patient together with a member of the research team using a basetech scale (conrad article number: 1283451-83) to weigh out the portion size (10 g). Packaging of the products in sachets will be done according to the relevant GMP guidelines and takes place during the first visit. The sachets will be labelled with: Study name, content sachet (WholeFiber™), research institute, expiration date and storing conditions. Subjects will receive an additional document stating the use of WholeFiber™ and the ingredients of the sachets. The outer box will contain contact details of the investigators.

6.8. Drug accountability

Patients receive the product at the first visit. The sachets (supplemented by WholeFiber™) will be filled by the patient together with a member of the research team using a basetech scale (conrad article number: 1283451-83) to weigh out the portion size (10 g). At home, subjects are asked to store the sachets at room temperature for the duration of the intervention period. Each subject will receive 90 sachets (including 6 reserve sachets). At each visit, the patient is asked to bring the remaining sachets, and the researcher will count how many sachets are left. A calculation is made to estimate whether all sachets are used on each day.

7. NON-INVESTIGATIONAL PRODUCT

Not applicable.

8. METHODS

8.1. Study parameters

8.1.1. Main study parameter

Effect of a high fiber prebiotic vegetable (WholeFiber™) for 6 weeks on fecal SCFA levels in intermediate to high-risk cutaneous melanoma patients, with no concurrent adjuvant treatment. HPLC ion chromatography system (Metrohm AG, Herisau, Switzerland) will be used to determine the levels of SCFA. The concentrations of SCFA; butyrate, propionate, and acetate will be measured with a conductivity detector. SCFA will be measured at baseline, halfway intervention and after 6 weeks.

8.1.2. Secondary study parameters

Discovering the gut microbial composition changes measured in intermediate to high-risk cutaneous melanoma patients with no concurrent adjuvant treatment, after using WholeFiber™ for 6 weeks. This analysis will be based on whole genome sequencing of fecal samples performed at the UMCG according to standardized protocol.

Exploring the effect of WholeFiber™ use for 6 weeks on immune functioning, stool patterns, fecal calprotectin levels and side effects in this patient group. Peripheral blood mononuclear cells (PBMCs) and bloodplasma will be isolated to determine immune cell composition before and after the intervention period. Fecal calprotectin will be determined using the respective ELISA kit. Calprotectin is released when neutrophils enter the gut wall and are activated during the inflammatory process²⁸. Lastly, eating patterns, fiber intake before the interventional period, stool patterns and side effects will be identified using the Food Frequency Questionnaire²⁹, Bristol Stool Scale³⁰, Gastrointestinal Symptoms Rating Scale³¹ and Health Related Quality of Life³² questionnaires.

8.1.3. Other study parameters

Anthropometry measurements at the baseline visit such as height, weight, BMI, waist circumference. We will extract demographic and disease progression data from patients' medical records. If data is missing in the medical records, additional information will be acquired by interviewing the patient during the clinical visit(s).

8.2. Randomization, blinding and treatment allocation

Not applicable, as it is an explorative study with one arm, where we are also interested in the tolerability of the product by this patient group.

8.3. Study procedures

8.3.1. Screening

Surgically treated intermediate to high-risk cutaneous melanoma patients with no concurrent adjuvant treatment will be notified about this explorative study by their treating physician. When the patient is interested, the coordinating investigator can explain the study and provide the patient with the patient information form (PIF). The patient and the study coordinator can discuss about the next steps in study participation. Written informed consent for participation in the trial must be obtained before performing any study specific screening tests or evaluation. All screening evaluations must be completed and reviewed to confirm that patients meet all eligibility criteria before enrollment.

8.3.2. Assessment of medical history and demographics

Medical history includes clinically significant diseases, surgeries, cancer history (including prior cancer therapies and procedures), reproductive status, smoking history, and all medications (e.g. prescription drugs, over-the-counter drugs, herbal or homeopathic remedies, nutritional supplements) used by the patient within 3 months prior to the screening visit. Demographic data will include age, sex, BMI, and self-reported race/ethnicity.

8.3.3. Blood sample collection

Blood will be collected at the medical oncology department of the UMCG using a standardized protocol. The drawing of blood will be performed by trained employees and the time of sampling will be recorded on a blood drawing form. Blood will be drawn from the antecubital vein in the arm. During each visit, 10 ml of blood will be collected for PBMC isolation and plasma measurements. Specific collection tubes that are used are CPT tubes.

Blood will then be transferred to the laboratory site and PBMC isolation will take place immediately. The average amount of cells that can be isolated is 1.30×10^6 PBMCs/ml. PBMCs and plasma will then be stored at -80°C , at the same laboratory site as the isolation, until analysis. PBMCs will be transferred to liquid nitrogen storage 24 hours after isolation of the PBMCs.

8.3.4. Laboratory assessments

Samples of venous blood drawn at each visit will be analyzed at the study site's local laboratory. Local laboratory assessments will include PBMC isolation and storage of plasma. By using flow cytometric analysis the immune cell composition will be determined (Table 1).

Table 1: Flowcytometry panel PBMC analysis

Marker	Fluorochrome	Clone	Cell Type	Marker Type
CD24	BUV395	ML5	Monocytes	Surface
CD27	BUV661	M-T271	Memory T cells	Surface
CD45	BUV737	HI30	Leukocytes	Surface
CD38	BUV805	HB7	Activated T cells	Surface
CD3	APC-H7	SK7	T cells, $\gamma\delta$ T cells	Surface
CD45RA	BV711	HI100	Naive T cells	Surface
CD4	BV785	OKT4	Helper T cells	Surface
FoxP3	AF488	259D	Regulatory T cells (Tregs)	Intracellular
CD8	PerCP/Cy5.5	SK1	Cytotoxic T cells	Surface
CD14	APC	HCD14	Monocytes	Surface
TNF	PE	MAb11	Inflammatory cytokine	Intracellular
IFNy	PE/Cy7	4S.B3	Cytokine in T cells	Intracellular
CD25	PE	BC96	Regulatory T cells (Tregs)	Surface
TCR $\gamma\delta$	FITC	B1.1	$\gamma\delta$ T cells	Surface
CD11c	BV605	3.9	Dendritic cells, monocytes	Surface
CD16	BV510	3G8	Non-classical monocytes	Surface

8.3.5. Fecal sampling

Three tubes of feces will be collected prior to the WholeFiber™ intervention, mid-trial, and at the end of the 6-week intervention period. After instructions, patients will collect their feces at home in a standardized manner. See section 15.2 for a detailed description of the stool sampling.

The stool samples must be stored in a (home) freezer within 10 minutes after collection. At the study visit, the stool samples will be brought by the participant in a cooler bag. These procedures are based on protocols used in Lifelines. After processing, the samples will be stored at -80°C at the Microbiome Hub (UMCG).

8.3.6. Analyses of fecal material

Collected tubes with feces samples will be stored (at -80°C) until a sufficient batch size is present for further analyses (calprotectin, microbiome, SCFAs). Analyses of the microbiome will be conducted within the UMCG following standardized procedures. The composition and function of the gut microbiome will be analyzed prior to, mid-trial, and after the WholeFiber™ intervention using whole genome sequencing. Temporal changes in the gut microbiome following the WholeFiber™ intervention can be traced up to species and even strain level by using novel algorithms³³. Analyses and interpretation of the microbiome will be in the context of patient characteristics (age, sex, BMI), and use of medication, including vitamins, probiotics, and homeopathic compounds.

HPLC ion chromatography system (Metrohm AG, Herisau, Switzerland) will be used for the short chain fatty acid analysis. The concentrations of SCFA (acetic acid, propionic acid, butyric acid, isobutyric acid, valeric acid, isovaleric acid, 2-methylbutyric acid, caproic acid) will be measured with a conductivity detector. The 6.1005.200 Metrosep Organic Acids column (Metrohm AG) with 5mm particle size and dimensions of 7.8 mm by 250 mm will be used for differentiating fatty acids. The mobile phase is 5mM HNO₃ and acetonitrile v/v ratio of 98:2, respectively, with a flow rate of 0.6 ml per minute.

Fecal calprotectin levels will be measured in the collected fecal samples (baseline, mid-trial, end of intervention) using Enzyme-Linked Immuno Sorbent Assay (ELISA).

8.3.7. Questionnaires

Subjects will complete the questionnaires prior to the study visit. After enrolment in the study, they will receive the questionnaires via post (physical or online), which need to be filled in prior to every study visit. This will take up to one hour. These questionnaires include:

- Food Frequency Questionnaire^{29,34} (FFQ)
- Health Related Quality of Life³² (HR-QoL)
- Bristol Stool Chart³⁰
- Gastrointestinal Symptom Rating Scale³¹ (GSRS)

8.3.8. Storage of samples

All patient related material (blood and feces) will be anonymized by using a unique patient identification code (see also section 12.1)

8.4. Withdrawal of individual subjects

Subjects can leave the study at any time for any reason if they wish to do so without any consequences. The investigator can decide to withdraw a subject from the study for urgent medical reasons. If subjects leave the study, their results (blood samples, fecal samples, and questionnaires) will be used for the analyses unless the patient specifically states that we may not use the collected data and material when signing the informed consent.

8.5. Specific criteria for withdrawal

Reasons for withdrawal from the study may include but are not limited to the following:

- Subject withdrawal of consent at any time;
- Any medical condition that the investigator determines may jeopardize the subject's safety if he or she continues in the study;
- Investigator determines it is in the best interest of the subject;
- Subject non-compliance.

8.6. Replacement of individual subjects after withdrawal

If subjects withdraw before the intervention has started, they will be replaced.

8.7. Premature termination of the study

The study is a short intervention study and we do not expect a premature termination. Since WholeFiber™ is suitable for human consumption, safe, and commercially available, we do not expect any negative events. Consumption of the product may result in uncomfortable though harmless effects such as increased flatulence or bloating. Research has shown that these adverse events are highly variable among people.

9. SAFETY REPORTING

9.1. Temporary halt for reasons of subject safety

In accordance with section 10, subsection 4 of the WMO, the sponsor will suspend the study if there is sufficient ground that continuation of the study will jeopardize the health or safety of the subjects participating in the study. The sponsor will notify the accredited METc without undue delay of a temporary halt including the reason for such an action. The study will be suspended pending a further positive decision by the accredited METc. The primary investigator will take care of the fact that all subjects are kept informed about the decisions.

9.2. AEs, SAEs and SUSARs

9.2.1. Adverse events (AEs)

Adverse events are defined as any undesirable experience occurring to a subject during the study, whether considered related to the investigational product. All adverse events reported spontaneously by the subject or observed by the investigator, will be recorded.

9.2.2. Serious adverse events (SAEs)

A serious adverse event is any untoward medical occurrence or effect that

- results in death;
- is life threatening (at the time of the event);
- requires hospitalization or prolongation of existing inpatients' hospitalization;
- results in persistent or significant disability or incapacity;
- is a congenital anomaly or birth defect;
- or any other important medical event that did not result in any of the outcomes listed above due to medical or surgical intervention but could have been based upon appropriate judgement by the investigator.

An elective hospital admission will not be considered as a serious adverse event.

The investigator will report the SAEs through the web portal *ToetsingOnline* to the accredited METc that approved the protocol, within 7 days of first knowledge for SAEs that result in death or are life threatening followed by a period of maximum of 8 days to complete the initial preliminary report. All other SAEs will be reported within a period of maximum 15 days after the sponsor has first knowledge of the serious adverse events.

9.3. Follow-up of adverse events

All AEs will be followed until they have abated, or until a stable situation has been reached. Depending on the event, follow up may require additional tests or medical procedures as indicated, and/or referral to the general physician or a medical specialist. SAEs need to be reported till end of study within the Netherlands, as defined in the protocol.

10. STATISTICAL ANALYSIS

Statistical analyses will be performed using R. In general, continuous data will be presented as mean \pm standard deviation (SD) or median and interquartile range when skewed, and categorical data as counts and percentages. To correctly model the paired pre-post study design, we will use a linear mixed-effects model (*lme4*-package, version 1.1-35.2, Bates et al., 2015). This is performed by adding a patient-specific intercept and slope. As this is an exploratory study, mean differences with a 95% confidence interval will be considered as statistically significant. A false discovery rate (FDR) of 5% will be used in regression analyses, regarding SCFA and bacterial taxa, to correct for multiple testing. We will adjust for differences in age, sex, BMI, and fiber intake before the start of the intervention by including these as independent variables in the linear mixed-effects models described below.

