2. OBJECTIVES

The primary objective of this study is to investigate the effect of dried chicory root (WholeFiberTM) for 6 weeks on fecal SCFA levels in intermediate to high-risk melanoma patients after surgical treatment with no concurrent adjuvant treatment.

Secondary objectives

- Exploration of the gut microbial composition of surgically treated intermediate to high-risk cutaneous melanoma patients before intake and potential compositional changes after using WholeFiberTM for 6 weeks.
- Exploration of the effect of WholeFiberTM use for 6 weeks on immune cell composition, stool patterns, fecal calprotectin levels and side effects in intermediate to high-risk cutaneous melanoma patients after surgical treatment, with no concurrent adjuvant treatment.

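### The 5% FDR covers only SCFA and bacterial taxa, so immune-cell results can be called significant from unadjusted 95% intervals, although section 4.4 disclaims significance

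*Protocol*

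**What the plan says.** Protocol section 10 sets two rules.

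- A general rule for reading results: "As this is an exploratory study, mean differences with a 95% confidence interval will be considered as statistically significant".
- A correction with a stated scope: "A false discovery rate (FDR) of 5% will be used in regression analyses, regarding SCFA and bacterial taxa, to correct for multiple testing".

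Section 2 lists as a secondary objective: "Exploration of the effect of WholeFiberTM use for 6 weeks on immune cell composition, stool patterns, fecal calprotectin levels and side effects". Section 8.1.2 says that blood cells and plasma "will be isolated to determine immune cell composition before and after the intervention period". Section 8.3.4 adds: "By using flow cytometric analysis the immune cell composition will be determined", with reference to Table 1, which has 16 marker rows. Blood is drawn at baseline, mid-trial and end of trial (sections 3 and 15.1).

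Three other statements bear on the point. Section 4.4 says that the study, with 20 participants and no sample size calculation, is not meant to reach significance and that paired differences with 95% intervals are enough. Section 10.1 defines a positive study by fecal SCFA alone. Sections 10.1 and 10.2 describe models for SCFA, taxa and diversity.

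**The concern.** The protocol recognises that exploratory results need multiplicity control, because it applies an FDR to SCFA and taxa within the same exploratory study. SCFA is a small family: three acids in section 8.1.1, eight in section 8.3.6. The immune panel could yield at least as many readouts, but the correction does not name it, and no reason is given for the difference. The only rule in section 10 that reaches immune data is the general one, which carries the word significant.

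Section 4.4 sharpens this. If its estimation aim governed throughout, the missing correction would matter little, because nobody would be declaring immune effects. Section 10 keeps the label, so it does matter.

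At stake is how the immune results are reported. Sections 1.3 and 1.4 present immune cells as part of the axis under study and as a reason for choosing this population. A chance change in one subset among 20 patients could be published as a significant effect of the fiber.

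**Working it through.** **Plan's own figure.** There is none to reproduce: the protocol gives no power, no familywise error rate and no count of immune tests.

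**Inputs.**
- Level per comparison: two-sided 0.05. This is my reading of the 95% interval rule; the text does not say that the interval must exclude zero.
- Sample size: 20, one arm (sections 4.4 and 8.2).
- Panel size: 16 rows in Table 1. They carry 14 distinct cell-type labels, since CD24 and CD14 share one and FoxP3 and CD25 share another.
- Number of immune readouts *k*: not stated. Values of 10, 14 and 16 are assumptions.
- Correlation between readouts: not stated. Assumed common value from 0 to 0.7.

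**Step 1: independent tests, no true change.** The chance of at least one false positive is 1 − 0.95^*k*, and the expected number is 0.05*k*.

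- *k* = 10: 1 − 0.95^10 = 40.1%, expected 0.5
- *k* = 14: 1 − 0.95^14 = 51.2%, expected 0.7
- *k* = 16: 1 − 0.95^16 = 56.0%, expected 0.8

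**Step 2: correlated tests.** I used 40,000 simulated null trials per setting with n = 20 and a paired t-test for each readout as a simple stand-in for the mixed model. Entries are the chance of at least one false positive. The last column applies Benjamini-Hochberg at 5% to the 16 readouts.

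| Correlation | k = 10 | k = 14 | k = 16 | k = 16, Benjamini-Hochberg |
|---|---|---|---|---|
| 0 | 40.4% | 51.1% | 56.4% | 5.2% |
| 0.2 | 37.7% | 48.1% | 52.4% | 5.0% |
| 0.3 | 35.5% | 44.6% | 48.5% | 4.8% |
| 0.5 | 29.7% | 36.6% | 38.5% | 4.3% |
| 0.7 | 21.8% | 26.1% | 27.4% | 3.5% |

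The simulated 56.4% at zero correlation agrees with the exact 56.0%. For 16 readouts the range is therefore about 27% to 56%.

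**Step 3: other counts.** Twenty independent tests would give 1 − 0.95^20 = 64.2%. Sixteen readouts tested at both mid-trial and end make 32 tests, or 1 − 0.95^32 = 80.6% if independent. Changes at the two visits share a baseline, so that last figure is an upper one. A short list of five would give 1 − 0.95^5 = 22.6% without any correction.

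**The case against.** The strongest objection is that the number of false positives is unknown, and that the tempting headline fails. A reader might infer from the 56% that a false immune finding is more likely than not. The documents do not support this. That figure needs 16 independent tests, one per antibody row, with no true effect anywhere. Table 1 lists markers, not endpoints. Markers are combined to define populations, CD45 and CD3 mark broad parent populations and may serve only for gating, and two pairs share a label. Readouts from one blood sample are likely to be correlated, and at a correlation of 0.3 even 16 tests fall below one half. This objection stands. The count could also be higher than 16, so the uncertainty runs both ways.

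Second, a statistical analysis plan that is not at hand may hold the immune endpoint list, model and correction. Their absence here is not a fault. What remains open to criticism is narrower: the protocol itself fixes the scope of the FDR and a significance rule that reaches beyond that scope.

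Third, the outcome is exploratory and decides nothing. A reader might infer that follow-up research hangs on the immune result. Section 13.1(c) instead ties the later randomized trial to the expected microbiota and SCFA effects. This stands and limits the severity. It does not remove the point, because the taxa are just as exploratory and do receive the correction.

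Fourth, a reader might take section 1.2 as a declared list of immune endpoints that section 10 forgot to use. It is background on mechanism, so using it as the test family is one option and not an obligation.

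**Conclusion.** The point holds as a minor one. As written, section 10 allows immune-cell differences to be called significant from unadjusted 95% intervals, while SCFA and taxa are held to a 5% FDR and section 4.4 says that significance is not sought.

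The size rests on assumptions: 16 readouts at one time point, no true change, a two-sided 5% level and a common correlation between 0 and 0.7. On these, the chance of at least one false significant immune result is about 27% to 56%. Even the low end is more than five times 5%. Fewer readouts lower the figure; more subsets or a second time point raise it. The conclusion that the chance is well above 5% does not depend on the exact count: ten readouts at a correlation of 0.7 still give about 22%.

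Severity is minor because immune composition is secondary and exploratory, and the definition of a positive study does not use it.

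**What to change.** Change section 10 by one sentence, choosing either of two equally acceptable options.

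1. **Extend the correction.** Add immune-cell populations to the FDR sentence as a separate 5% family, with the populations listed in advance. A short list limits the loss of power. The populations discussed in section 1.2 (regulatory T cells, TNF- and IFN-γ-producing CD4+ cells, CD8+ cells, γδ T cells) are one possible list. Subsets outside it would be reported as estimates with intervals only.
2. **Drop the label.** State that immune results are reported as paired differences with 95% intervals and are not described as significant, which brings section 10 into line with section 4.4.

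The first option costs some power per subset. Under Benjamini-Hochberg the smallest p-value, if it stands alone, must reach 0.05/16 = 0.003 in a family of 16, but only 0.05/5 = 0.01 in a family of five. The second costs only the significance label, which section 4.4 says the study does not need. Neither changes data collection or the primary analysis.
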